11.1.3 Methods for Evaluation of Disease

All measurements should be taken and recorded in metric notation using a ruler, calipers, or a digital measurement tool. All baseline evaluations should be performed as closely as possible to the beginning of treatment and never more than 4 weeks before the beginning of the treatment.

The same method of assessment and the same technique should be used to characterize each identified and reported lesion at baseline and during follow-up. Imaging-based

evaluation is preferred to evaluation by clinical examination unless the lesion(s) being followed cannot be imaged but are assessable by clinical exam.

Clinical lesions. Clinical lesions will only be considered measurable when they are superficial (e.g., skin nodules and palpable lymph nodes) and ≥ 10 mm in diameter as assessed using calipers (e.g., skin nodules). In the case of skin lesions, documentation by color photography, including a ruler to estimate the size of the lesion, is recommended.

Chest x-ray. Lesions on chest x-ray are acceptable as measurable lesions when they are clearly defined and surrounded by aerated lung; however, CT is preferable.

Conventional CT and MRI. This guideline has defined measurability of lesions on CT scan based on the assumption that CT thickness is 5mm or less. If CT scans have slice thickness greater than 5 mm, the minimum size of a measurable lesion should be twice the slice thickness. MRI is also acceptable in certain situations (e.g. for body scans).

Use of MRI remains a complex issue. MRI has excellent contrast, spatial, and temporal resolution; however, there are many image acquisition variables involved in MRI, which greatly impact image quality, lesion conspicuity, and measurement. Furthermore, the availability of MRI is variable globally. As with CT, if an MRI is performed, the technical specifications of the scanning sequences used should be optimized for the evaluation of the type and site of disease. Furthermore, as with CT, the modality used at follow-up should be the same as was used at baseline and the lesions should be measured/assessed on the same pulse sequence. It is beyond the scope of the RECIST guidelines to prescribe specific MRI pulse sequence parameters for all scanners, body parts, and diseases. Ideally, the same type of scanner should be used and the image acquisition protocol should be followed as closely as possible to prior scans. Body scans should be performed with breath-hold scanning techniques, if possible.

FDG-PET. While FDG-PET response assessments need additional study, it is sometimes reasonable to incorporate the use of FDG-PET scanning to complement CT scanning in assessment of progression (particularly possible 'new' disease). New lesions on the basis of FDG-PET imaging can be identified according to the following algorithm:

- (a) Negative FDG-PET at baseline, with a positive FDG-PET at follow-up is a sign of PD based on a new lesion.
- (b) No FDG-PET at baseline and a positive FDG-PET at follow-up: If the positive FDG-PET at follow-up corresponds to a new site of disease confirmed by CT, this is PD. If the positive FDG-PET at follow-up is not confirmed as a new site of disease on CT, additional follow-up CT scans are needed to determine if there is truly progression occurring at that site (if so, the date of PD will be the date of the initial abnormal FDG-PET scan). If the positive FDG-PET at follow-up corresponds to a pre-existing site of disease on CT that is not progressing on the basis of the anatomic images, this is not PD.
- (c) FDG-PET may be used to upgrade a response to a CR in a manner similar to a biopsy in cases where a residual radiographic abnormality is thought to represent fibrosis or scarring. The use of FDG-PET in this circumstance should be

prospectively described in the protocol and supported by disease-specific medical literature for the indication. However, it must be acknowledged that both approaches may lead to false positive CR due to limitations of FDG-PET and biopsy resolution/sensitivity.

Note: A ‘positive’ FDG-PET scan lesion means one which is FDG avid with an uptake greater than twice that of the surrounding tissue on the attenuation corrected image.

PET-CT. At present, the low dose or attenuation correction CT portion of a combined PET-CT is not always of optimal diagnostic CT quality for use with RECIST measurements. However, if the site can document that the CT performed as part of a PET-CT is of identical diagnostic quality to a diagnostic CT (with IV and oral contrast), then the CT portion of the PET-CT can be used for RECIST measurements and can be used interchangeably with conventional CT in accurately measuring cancer lesions over time. Note, however, that the PET portion of the CT introduces additional data which may bias an investigator if it is not routinely or serially performed.

Cytology, Histology. These techniques can be used to differentiate between partial responses (PR) and complete responses (CR) in rare cases (e.g., residual lesions in tumor types, such as germ cell tumors, where known residual benign tumors can remain).

The cytological confirmation of the neoplastic origin of any effusion that appears or worsens during treatment when the measurable tumor has met criteria for response or stable disease is mandatory to differentiate between response or stable disease (an effusion may be a side effect of the treatment) and progressive disease.

11.1.4 Response Criteria

11.1.4.1 Evaluation of Target Lesions

Complete Response (CR): Disappearance of all target lesions. Any pathological lymph nodes (whether target or non-target) must have reduction in short axis to <10 mm.

Partial Response (PR): At least a 30% decrease in the sum of the diameters of target lesions, taking as reference the baseline sum diameters.

Progressive Disease (PD): At least a 20% increase in the sum of the diameters of target lesions, taking as reference the smallest sum on study (this includes the baseline sum if that is the smallest on study). In addition to the relative increase of 20%, the sum must also demonstrate an absolute increase of at least 5 mm. (Note: the appearance of one or more new lesions is also considered progressions).

Stable Disease (SD): Neither sufficient shrinkage to qualify for PR nor sufficient increase to qualify for PD, taking as reference the smallest sum diameters while on study.

11.1.4.2 Evaluation of Non-Target Lesions

Complete Response (CR): Disappearance of all non-target lesions and normalization of tumor marker level. All lymph nodes must be non-pathological in size (<10 mm short axis).

Note: If tumor markers are initially above the upper normal limit, they must normalize for a patient to be considered in complete clinical response.

Non-CR/Non-PD: Persistence of one or more non-target lesion(s) and/or maintenance of tumor marker level above the normal limits.

Progressive Disease (PD): Appearance of one or more new lesions and/or *unequivocal progression* of existing non-target lesions. *Unequivocal progression* should not normally trump target lesion status. It must be representative of overall disease status change, not a single lesion increase.

Although a clear progression of “non-target” lesions only is exceptional, the opinion of the treating physician should prevail in such circumstances, and the progression status should be confirmed at a later time by the review panel (or Principal Investigator).

11.1.4.3 Evaluation of New Lesions

The finding of a new lesion should be unequivocal (i.e. not due to difference in scanning technique, imaging modality, or findings thought to represent something other than tumor (for example, some ‘new’ bone lesions may be simply healing or flare of pre-existing lesions). However, a lesion identified on a follow-up scan in an anatomical location that was not scanned at baseline is considered new and will indicate PD. If a new lesion is equivocal (because of small size etc.), follow-up evaluation will clarify if it truly represents new disease and if PD is confirmed, progression should be declared using the date of the initial scan on which the lesion was discovered.

11.1.4.4 Evaluation of Best Overall Response

The best overall response is the best response recorded from the start of the treatment until disease progression/recurrence (taking as reference for progressive disease the smallest measurements recorded since the treatment started). The patient's best response assignment will depend on the achievement of both measurement and confirmation criteria.

For Participants with Measurable Disease (*i.e.*, Target Disease)

Target	Non-Target	New	Overall	Best Overall Response when
--------	------------	-----	---------	----------------------------

Lesions	Lesions	Lesions	Response	Confirmation is Required*
CR	CR	No	CR	≥4 wks Confirmation**
CR	Non-CR/Non-PD	No	PR	
CR	Not evaluated	No	PR	
PR	Non-CR/Non-PD/not evaluated	No	PR	≥4 wks Confirmation**
SD	Non-CR/Non-PD/not evaluated	No	SD	Documented at least once ≥4 wks from baseline**
PD	Any	Yes or No	PD	
Any	PD***	Yes or No	PD	
Any	Any	Yes	PD	no prior SD, PR or CR

* See RECIST 1.1 manuscript for further details on what is evidence of a new lesion.
** Only for non-randomized trials with response as primary endpoint.
*** In exceptional circumstances, unequivocal progression in non-target lesions may be accepted as disease progression.

Note: Participants with a global deterioration of health status requiring discontinuation of treatment without objective evidence of disease progression at that time should be reported as “*symptomatic deterioration*.” Every effort should be made to document the objective progression even after discontinuation of treatment.

For Participants with Non-Measurable Disease (*i.e.*, Non-Target Disease)

Non-Target Lesions	New Lesions	Overall Response
CR	No	CR
Non-CR/non-PD	No	Non-CR/non-PD*
Not all evaluated	No	not evaluated
Unequivocal PD	Yes or No	PD
Any	Yes	PD

* ‘Non-CR/non-PD’ is preferred over ‘stable disease’ for non-target disease since SD is increasingly used as an endpoint for assessment of efficacy in some trials so to assign this category when no lesions can be measured is not advised

11.1.5 Duration of Response

Duration of overall response: The duration of overall response is measured from the time measurement criteria are met for CR or PR (whichever is first recorded) until the first date that recurrent or progressive disease is objectively documented (taking as reference for progressive disease the smallest measurements recorded since the treatment started, or death due to any cause. Participants without events reported are censored at the last disease evaluation).

Duration of overall complete response: The duration of overall CR is measured from the time measurement criteria are first met for CR until the first date that progressive disease is objectively documented, or death due to any cause. Participants without events reported are censored at the last disease evaluation.

Duration of stable disease: Stable disease is measured from the start of the treatment until the criteria for progression are met, taking as reference the smallest measurements recorded since the treatment started, including the baseline measurements.

11.1.6 Progression-Free Survival

Overall Survival: Overall Survival (OS) is defined as the time from registration to death due to any cause, or censored at date last known alive.

Progression-Free Survival: Progression-Free Survival (PFS) is defined as the time from registration to the earlier of progression or death due to any cause. Participants alive without disease progression are censored at date of last disease evaluation.

Time to Progression: Time to Progression (TTP) is defined as the time from randomization (or registration) to progression, or censored at date of last disease evaluation for those without progression reported.

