4. REGISTRATION PROCEDURES

4.1 General Guidelines for DF/HCC Institutions

Institutions will register eligible participants in the Clinical Trials Management System (CTMS) OnCore. Registrations must occur prior to the initiation of protocol therapy. Any participant not registered to the protocol before protocol therapy begins will be considered ineligible and registration will be denied.

An investigator will confirm eligibility criteria and a member of the study team will complete the protocol-specific eligibility checklist.

Following registration, participants may begin protocol therapy. Issues that would cause treatment delays should be discussed with the Overall Principal Investigator (PI). If a participant does not receive protocol therapy following registration, the participant's registration on the study must be canceled. Registration cancellations must be made in OnCore as soon as possible.

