Extracranial PFS and Intracranial PFS: Extracranial PFS (EPFS) is defined as the time from first dose of study drug to documented extracranial progression (per RECIST or irRC) or death, whichever occurs first. Intracranial PFS (IPFS) is defined as the time from first dose of ipilimumab and nivolumab to documented intracranial progression (RANO) or death, whichever occurs first. For both endpoints, the follow-up of patients who have neither died nor progressed at the time of analysis will be censored at the date of last adequate disease assessment. Each cohort will be presented separately. Median EPFS and IPFS will be presented and accompanied by 90% confidence intervals estimated using log(-log(survival)) methodology. Point estimates at 3 and 6 months will also be presented with confidence intervals.

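### OS3 is counted from registration but only treated patients are counted, so the wait for the first dose is assured survival time; EPFS and IPFS run from first dose

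*Combined protocol and SAP*

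**What the plan says.** Section 11.1.6 holds the only OS definition in the document: "Overall Survival (OS) is defined as the time from registration to death due to any cause, or censored at date last known alive". It gives PFS the same origin: "Progression-Free Survival (PFS) is defined as the time from registration to the earlier of progression or death due to any cause".

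Section 13.6 uses a different origin for the two PFS endpoints that the trial analyses. For one, "Extracranial PFS (EPFS) is defined as the time from first dose of study drug to documented extracranial progression"; for the other, "Intracranial PFS (IPFS) is defined as the time from first dose of ipilimumab and nivolumab to documented intracranial progression".

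Sections 13.1, 13.2 and 13.5 name OS3 as the primary endpoint without saying when the three months start, so the definition in 11.1.6 governs.

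Two rules decide who is counted. Section 4.1 places registration before therapy and adds: "If a participant does not receive protocol therapy following registration, the participant's registration on the study must be canceled". Section 13.8.2 admits to the primary assessment only patients who received at least one cycle.

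**The concern.** Taken together, these rules credit time in which no counted patient can fail. A patient who dies after registration but before the first dose loses the registration and is also outside the set in 13.8.2. Everyone left has survived that interval, and the interval still counts toward the three months. The rule in 13.2 and 13.5 that treats unknown vital status as death does not help, because these patients are not in the denominator.

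The disease is fast: section 2.1 puts untreated median survival at about 4 to 6 weeks, and section 3.1.4 asks only for a life expectancy above 3 weeks. The decision rule has little slack: 6 of 18 alive is a success and 5 is not. If the 18% null rate was measured from start of treatment, a few days of assured survival would lift the OS3 expected of an ineffective treatment above 18%, and the false-positive rate with it. With the origin of OS3 left to inference, one death near day 91 could also change the result according to which origin the analyst picks.

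**Working it through.** **Inputs from section 13.2.** Null 18%, alternative 43%; 9 patients in stage 1, stop if 0 or 1 are alive; 18 in total, success if 6 or more are alive. Stated type I error 8% (target 10%), power 86% (target 85%), early-stop probability 0.50 under the null.

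**Step 1: the plan's own figures.** With p the chance that a counted patient is alive at 3 months,

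P(success) = sum over x = 2 to 9 of P(X1 = x) × P(X2 ≥ 6 − x), where X1 and X2 are both Binomial(9, p).

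At p = 0.18:
- x = 2: 0.2908 × 0.0615 = 0.0179
- x = 3: 0.1489 × 0.2105 = 0.0313
- x = 4: 0.0490 × 0.5012 = 0.0246
- x = 5: 0.0108 × 0.8324 = 0.0090
- x = 6 to 9: 0.0017

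The sum is 0.0845, which agrees with the stated 8%. The early-stop probability is 0.499, which agrees with 0.50. Two-stage power at 43% is 84.2%. The stated 86% is what 6 of 18 gives without the interim stop (85.7%); this does not affect the present point.

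**Step 2: assumptions the documents do not supply.**
- The 18% runs from start of treatment.
- Three months is 91 days.
- Every patient has the same gap of d days between registration and first dose.
- Survival from first dose is exponential. With 18% alive at day 91, the median is 91 × ln 2 / ln(1/0.18) = 36.8 days, about 5.3 weeks, inside the range in section 2.1.

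**Step 3: effect of the gap.** Counted from registration, a patient needs to survive only 91 − d days after the first dose, so the null rate becomes 0.18^((91 − d)/91). For d = 7 this is 0.18^0.9231 = 0.205. Each rate then goes through the formula in step 1.

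| Gap (days) | Null OS3 from registration | Early stop under null | Type I error |
|---|---|---|---|
| 0 | 18.0% | 0.499 | 8.5% |
| 1 | 18.3% | 0.488 | 9.1% |
| 2 | 18.7% | 0.477 | 9.8% |
| 3 | 19.1% | 0.466 | 10.5% |
| 7 | 20.5% | 0.420 | 14.0% |
| 14 | 23.4% | 0.340 | 22.0% |

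**Step 4: sensitivity to the curve.** For a Weibull curve with shape k, also fixed at 18% on day 91, the null rate is 0.18^(((91 − d)/91)^k).

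| Gap (days) | k = 0.7 (falling hazard) | k = 1 | k = 1.3 (rising hazard) |
|---|---|---|---|
| 3 | 9.9% | 10.5% | 11.2% |
| 7 | 12.1% | 14.0% | 16.0% |
| 14 | 17.1% | 22.0% | 27.6% |

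**The case against.** A reader might infer that the trial runs at a false-positive rate of 14% or 22%. The documents do not support that, for three reasons.

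- **The gap may be short.** Section 5.2.1 uses Day 1 laboratory results to confirm eligibility, and section 4.1 has eligibility confirmed around registration, which places registration close to Day 1. The pregnancy test is tied to within 72 hours of enrolment in 5.2.1 and of the first dose in section 10. This is not conclusive, since section 10 lets screening assessments taken up to 14 days earlier serve as Day 1 assessments, and no maximum gap is set. But 14 days for every patient is the whole screening window, and gaps of 0 to 2 days keep the exponential figure under 10%.
- **The benchmark's origin is unknown.** If the 18% was counted from registration among treated patients, null and observed rates carry the same assured time and the comparison is not biased in this way.
- **The curve is a choice.** Eligibility covers any solid tumour, so a falling hazard is plausible, and it shrinks the effect.

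A reader might also infer that the secondary PFS analyses are undefined. They are not: 13.6 gives EPFS and IPFS explicit origins. The general PFS definition sits beside a time-to-progression definition that mentions randomisation in a single-arm trial, which looks like template text. The conflict reaches mainly the biomarker analyses in 13.7, which refer to PFS without saying which one. Using different origins for OS and PFS is not in itself an error.

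All of this limits the size. It does not remove the mismatch between the OS3 clock and the patients counted, which follows from the text alone.

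**Conclusion.** The point holds in a conditional form. The two origins, and the fact that no counted patient can die between registration and first dose, follow from 4.1, 11.1.6, 13.6 and 13.8.2 without any assumption. Whether this biases the primary test depends on the origin of the 18%: it favours the treatment if that rate runs from start of treatment, and not if it was counted from registration among treated patients.

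Under the first reading and an exponential curve, the 10% target is passed at a gap of about 3 days. At that gap, Weibull shapes 0.7 to 1.3 span 9.9% to 11.2%, so even the crossing point depends on the curve. The documents do not establish that the target is exceeded in fact.

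The one-cycle rule in 13.8.2 is a separate and possibly larger source of assured time. If it means a completed six-week cycle, 42 assured days put the null at 0.18^(49/91) = 39.7% and the type I error at about 77% under the same exponential assumption. Changing time zero does not cure that.

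**What to change.** In 11.1.6 and 13.5, define OS3, OS and PFS from the date of first dose, which matches 13.6 and the treated-only population. In 13.2, give the source of the 18% and state that it uses the same origin.

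The cost is a few sentences. OS3 becomes slightly harder to reach, because each patient must survive longer by the length of the gap. If the 43% alternative also runs from first dose, power is 84.2%, against 89.3% when a 7-day gap is credited (exponential assumption).

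The alternative is to keep registration as the origin throughout and count every registered patient, with deaths before dosing as failures. That costs more: 4.1 and 13.8.2 would have to change, as well as the EPFS and IPFS definitions in 13.6 if all endpoints are to share one origin.

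Under the first option, the one-cycle condition in 13.8.2 still has to be addressed separately.

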11.2 Antitumor Effect – Intracranial lesion assessments

For the purposes of this study, participants should be re-evaluated for intracranial response every 6 weeks. In addition to a baseline scan, confirmatory scans should also be obtained at 4 weeks following initial documentation of objective response. Response and progression will be evaluated in this study using the modified RANO Response Criteria.

11.2.1 Definitions

Evaluable for objective response. Only those participants who have measurable CNS disease present at baseline, have received at least one cycle of therapy, and have had their disease re-evaluated will be considered evaluable for target disease response in the CNS. These participants will have their response classified according to the definitions stated below. (Note: Participants who exhibit objective disease progression prior to the end of cycle 1 will also be considered evaluable.)

Evaluable non-measurable evaluable disease. Participants who have lesions present at baseline that are evaluable but do not meet the definitions of measurable disease, have received at least one cycle of therapy, and have had their disease re-evaluated will be considered evaluable for non-target disease. The response assessment is based on the presence, absence, or unequivocal progression of the lesions.

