11.2.4 Response Criteria

11.2.4.1 Evaluation of Intracranial Lesions

Complete Response (CR): Requires all of the following:

- complete disappearance of all enhancing measurable and nonmeasurable disease sustained for at least 4 weeks
- no new lesions
- stable or decreasing corticosteroids (the steroid dose at the time of the scan evaluation should be no greater than the dose at time of baseline scan)
- stable or improved clinically

Participants with non-measurable disease cannot have a complete response. The best possible response is stable disease.

Partial Response (PR): All of the following criteria must be met:

- Greater than or equal to 50% decrease compared to baseline in the sum of products of perpendicular diameters of all measurable enhancing lesions sustained for at least 4 weeks. In the absence of a confirming scan 4 weeks later, this scan will be considered only stable disease.
- no progression of non-measurable disease.
- no new lesions
- stable or reduced corticosteroid dose (the steroid dose at the time of the scan evaluation should be no greater than the dose at time of baseline scan)
- stable or improved clinically

Progressive Disease (PD): At least one of the following must be true:

- $\geq 25\%$ increase in the sum of products of all measurable lesions over smallest sum observed (over baseline if no decrease) using the same techniques as baseline
- clear worsening of any nonmeasurable disease*
- appearance of any new enhancing lesion/site
- clear clinical worsening (unless clearly unrelated to this cancer, e.g. seizures, medication side effects, complications of therapy, cerebrovascular events, infection)
- failure to return for evaluation due to death or deteriorating condition

* Progression of non-measurable CNS lesions is defined as follows:

- a lesion initially at baseline $\leq 5\text{mm}$ in diameter that increases to $\geq 10\text{mm}$ in diameter, or
- a lesion initially at baseline 6-9 mm in diameter that increases by at least 5 mm in diameter.

Stable Disease (SD): All of the following criteria must be met:

- Does not qualify for CR, PR or progression
- All measurable and non-measurable sites must be assessed using the same techniques as baseline
- Stable clinically.

A summary of the response criteria is in the below:

	Complete Response	Partial Response	Stable Disease	Progressive Disease
T1-Gd+	None	$\geq 50\%$ decrease	$<50\%$ decrease- $<25\%$ increase	$\geq 25\%$ increase*
New Lesion	None	None	None	Present*

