13.6 Analysis of Secondary Endpoints

Safety and Tolerability: All adverse events recorded during the trial will be summarized for all patients having received one or more doses of ipilimumab and nivolumab. The data for each cohort will be summarized separately, although safety data may be combined, if appropriate. The proportions of patients with grade-3 or higher hematologic toxicities or grade-3 or higher neurologic toxicities will be presented with 90% exact binomial confidence intervals. The incidence of events that are new or worsening from the time of first dose of treatment will be summarized according to system organ class and/or preferred term, severity (based on CTCAE grade), type of adverse event, and relation to study treatment. Deaths reportable as SAEs and non-fatal serious adverse events will be listed by patient and tabulated by primary system organ class, and type of adverse event.

Intracranial/Extracranial Response: The proportion of patients with intracranial response of intraparenchymal brain metastases (CR or PR by RANO) will be presented with a two-sided, 90% exact binomial confidence interval. For a sample of 18 patients, the confidence interval will have maximum width of 0.42. Extracranial response rates (CR or PR) according to RECIST and irRC will be summarized. Rates will be accompanied by two-sided 90% exact binomial

confidence intervals. Cases where RECIST and irRC responses do not agree will be documented.

Leptomeningeal Disease Response: The proportion of patients with leptomeningeal disease response (CR or PR) will be presented with a two-sided, 90% exact binomial confidence interval. For a sample of 18 patients, the confidence interval will have maximum width of 0.42.

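### Patients who die or decline without a post-baseline MRI can drop out of the intracranial response denominator, because 11.2.1, 11.2.4.1 and 13.6 do not settle whether they count

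*Combined protocol and SAP*

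**What the plan says.** Section 11.2.1 restricts evaluability for intracranial objective response to participants who "have measurable CNS disease present at baseline, have received at least one cycle of therapy, and have had their disease re-evaluated". It then says: "These participants will have their response classified according to the definitions stated below". A note in the same paragraph adds one exception: "Participants who exhibit objective disease progression prior to the end of cycle 1 will also be considered evaluable".

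Section 11.2.4.1 lists the events that make a patient progressive in the CNS. One of them is "failure to return for evaluation due to death or deteriorating condition".

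Section 13.6 gives the analysis: "The proportion of patients with intracranial response of intraparenchymal brain metastases (CR or PR by RANO) will be presented with a two-sided, 90% exact" binomial interval. It adds: "For a sample of 18 patients, the confidence interval will have maximum width of 0.42". It names no analysis set for this endpoint. Section 13.8 sets inclusion rules for toxicity and for the primary endpoint only.

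Timing comes from three other places. A cycle is 6 weeks outside some maintenance phases (5.1), intracranial disease is reassessed every 6 weeks (11.2), and entry requires a life expectancy of more than 3 weeks (3.1.4).

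**The concern.** Take a patient with a measurable brain metastasis who dies or declines in week 4 without a scan. Under 11.2.4.1 this patient is progressive, and so a non-responder. Under 11.2.1 the same patient has neither a completed cycle nor a re-evaluation. Unless the exception applies, the patient is not evaluable and is never classified.

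The two outcomes give different response rates. An intracranial response needs a post-baseline scan, so every patient lost this way would have been a non-responder. Removing such patients lowers the denominator and leaves the numerator unchanged. Secondary objective 2 could then describe only patients who lived long enough to be rescanned. Early loss is likely here, because the first assessment falls at 6 weeks and 13.2 expects a median survival of about 2-4 months.

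**Working it through.** **1. The plan's own figure.** Clopper-Pearson 90% limits are Beta(0.05; x, n−x+1) and Beta(0.95; x+1, n−x). For n = 18 the widest interval is at x = 9, with width 0.4176. This matches the stated 0.42, so no printed number is wrong.

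**2. The texts side by side.**

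| Patient without a post-baseline MRI | 11.2.4.1 | 11.2.1 |
|---|---|---|
| Dies or declines before the end of cycle 1 | Progressive | Evaluable only if this progression counts as objective, which is not stated |
| Dies or declines after cycle 1, before the scan | Progressive | Not re-evaluated; the exception has expired |

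The nearest guide to what objective means is in the extracranial criteria. Section 11.1.4.4 says that participants whose general health declines and who stop treatment "without objective evidence of disease progression at that time should be reported as" having symptomatic deterioration. That separates decline from objective progression and favours exclusion, but it is not written for the intracranial endpoint.

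**3. How many patients could be affected.** The documents give no week-6 mortality, no expected response rate and no number with measurable brain metastases. I assume exponential survival, and early death independent of having measurable lesions.

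From the median in 13.2, with 6 weeks = 42/30.44 = 1.380 months and S(6 weeks) = 0.5^(1.380/median):

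- Median 2 months: S = 0.620, so 38% die before week 6.
- Median 4 months: S = 0.787, so 21% die before week 6.

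From the 3-month survival hypotheses in 13.2, with S(6 weeks) = OS3^(6/13):

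- OS3 = 43%: S = 0.677, so 32% die before week 6.
- OS3 = 18%: S = 0.453, so 55% die before week 6.

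**4. Effect on the rate.** Suppose the true rate is 20%, counting early deaths as non-responders, and a share q of the early deaths leaves the denominator. The observed rate is then 0.20 / [1 − q(1 − S)].

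| Survival assumption | q = 1 | q = 0.5 | q = 0 |
|---|---|---|---|
| Median 2 months | 0.20/0.620 = 32% | 0.20/0.810 = 25% | 20% |
| Median 4 months | 0.20/0.787 = 25% | 0.20/0.8935 = 22% | 20% |
| OS3 = 18% | 0.20/0.453 = 44% | 0.20/0.727 = 28% | 20% |

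The column q = 0 is the reading in which progression by failure to return counts as evaluable. Values between 0 and 1 allow for early deaths that had documented objective progression first.

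**5. Precision.** Eligibility (3.1) requires carcinomatous meningitis, not measurable parenchymal metastases, so fewer than 18 patients may contribute. The maximum 90% width is 0.42 for n = 18, 0.51 for n = 12 and 0.61 for n = 8.

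**The case against.** The strongest reply is that nothing conflicts. The exception in 11.2.1 keeps early progressors evaluable, 11.2.4.1 defines progression to include failure to return, and together they keep early deaths in the denominator as progressive. Section 13.6 also speaks of patients without restriction and quotes a width for 18, which points towards counting everyone. This reading is possible, and it rules out saying that the two sections flatly contradict each other. It does not close the gap. The word objective is left undefined, its use in 11.1.4.4 points the other way, and the exception ends with cycle 1. The 18 in 13.6 cannot be taken as the denominator either, because the endpoint concerns brain metastases that eligibility does not require.

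A second reply is that the consequence is limited. The endpoint is secondary and descriptive, with no test or decision rule attached. Deaths are also events in intracranial PFS (13.6), and the primary endpoint is not governed by 11.2.1. This stands, and it limits the weight of the point.

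Two stronger readings are tempting. A reader might infer that the plan commits to analysing only rescanned patients, so that the reported rate will be inflated. The documents support only that it can be. A reader might also take the 2-4 month figures as a ceiling, or apply them to 18 patients. Neither is supported: the null OS3 implies more early deaths, living patients who are never rescanned are not counted, and the number with measurable lesions is not given.

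**Conclusion.** The point holds as a gap in the definition. The protocol does not settle whether patients who die or decline without a post-baseline MRI belong in the intracranial response denominator. Exclusion is the likelier reading of 11.2.1, but not a certain one. Any bias from exclusion is upward.

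Under the assumptions above, with a 2-4 month median, a true 20% could read anywhere from 20% (none excluded) to 32% (all excluded, 2-month median). Excluding half of the early deaths gives 25% to 22%. At the null OS3 of 18%, full exclusion would give 44%. The size depends on the assumed survival curve, the assumed 20% rate and the share of early deaths without documented objective progression. The point deserves correction because the denominator could otherwise be chosen after the data are seen, but it does not touch the primary analysis.

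**What to change.** In 11.2.1 and 13.6, define the intracranial response denominator as all treated patients with measurable CNS disease at baseline. Count death, deterioration or absence of a post-baseline MRI as non-response, which is consistent with 11.2.4.1. Report the set with at least one cycle and a re-evaluation only as a secondary description. In 13.6, replace the interval width for 18 patients with the width for the number expected to have measurable brain metastases, and state that number.

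The cost is wording in the protocol and its statistical section, with no new data and no change to visits. The downside is a somewhat lower reported response rate and, if fewer than 18 patients are expected to contribute, a wider stated interval.
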